- g: Weight and Height (without shoes) will be measured. Three measurements should be taken at each visit. Each measurement should be recorded as a separate entry on the Vital Sign eCRF.
- h: Only for those subjects who continue into Extension A.
- i: Unused study drug to be retrieved and study drug dispensed only for subjects requiring dose increases at Unscheduled Visits.
- j: Clinical laboratory tests include hematology, blood chemistry including lipid panel, and urinalysis.
- k: Fasting lipid and glucose samples to be taken at baseline and at end of treatment or early discontinuation, with fasting window (interval) between 2 and 4 hours.
- l: Female subjects age 8 years old and above, or of childbearing potential, only. If urine can not be obtained for pregnancy testing after screening, a serum pregnancy test will be performed. (revised per Amendment 01)
- m: Only for subjects aged 6 years and older at the time of consent/assent.
- n: If subject has a normal ECG baseline reading, but during any visit thereafter, the QT is measured as greater than 450 ms, 3 consecutive ECGs separated by 5 to 10 minutes will be performed to confirm the abnormality.
- o: During Unscheduled Visits, ECG or EEG will only be done if the results from the previous visit were deemed clinically significant by the investigator.
- p: EEG will be performed at awake and sleep state for all subjects.
- q: One blood sample (approximately 1 mL) for determination of perampanel plasma concentrations will be collected at any time during each of the specified visits.

Table 4 Schedule of Procedures/Assessments in Study E2007-G000-311: Core Study

Phase	Pre-Treatment	Treatment Phase									Early Discontinuation ^d	Unscheduled
	Screening/Baseline	Titration ^a				Maintenance ^b				Follow-up ^{b,c}		
Visit	1	2	3	4	5	6	7	8	9			
Week	From up to -4 weeks ±3 days to Week 0 (outside of Japan) -4 weeks ±3 days to Week 0 (Japan only) (revised per Amendment 02)	0	2	5	8	11	15	19	23	27		
Procedures/Assessments												

- r: Additional blood (approximately 1 mL/sample) will be drawn at the 1st report (where possible) of a serious adverse event or severe unexpected AE and at its resolution. (revised per Amendment 01)

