Height ^f		X	X		X	
Adverse events	X	X	X	X	X	X
IxRS call	X	X		X	X	X
Study drug compliance	X	X	X		X	X
Dispense study drug	X	X				X ^g
Retrieve unused study drug	X	X	X		X	X ^g
Dispense subject's diary	X	X				X
Retrieve and review diary	X	X	X	X	X	X
Clinical laboratory tests ^h		X	X ⁱ		X	X ^j
Thyroid (TSH, fT3, fT4) and IGF-1 testing			X		X	
Urine pregnancy test ^k	X	X	X	X	X	X
C-SSRS ^l	X	X	X	X	X	X
12-lead ECG ^m			X		X	X ⁿ
EEG ^o			X		X	X ⁿ
Telephone call ^p	X	X	X			
ABNAS ^q			X		X	
Lafayette Grooved Pegboard Test			X		X	
CBCL			X		X	
EQ-5D-Y			X		X	
Clinical Global Impression			X		X	
Disposition			X		X	

ABNAS = A-B neuropsychological assessment schedule, AE = adverse event, AED(s) = antiepileptic drug(s), CBCL = Child Behavior Checklist, C-SSRS = Columbia-Suicide Severity Rating Scale, eCRF = electronic case report form, EQ-5D-Y = EuroQol 5 Dimensions-Youth, fT3 = free triiodothyronine, fT4 = free thyroxine, IGF-1 = insulin-like growth factor-1, IxRS = interactive and response system, QTc = corrected QT interval, TSH = thyroid-stimulating hormone.

- a: All visits to be done within ±6 days of the schedule. (revised per Amendment 02)
- b: Follow-up Visit should be conducted 4 weeks (±7 days) after the last dose of study drug for all subjects, except for those subjects entering into Extension B. (revised per Amendment 04)
- c: Subjects should roll-over into Extension A immediately after completion of the Treatment Phase of the Core Study. Additional assessments to be done for subjects who choose to roll-over into Extension A.
- d: For any other clinic visits during the study, the physical and the neurological exams will only be performed when there is a complaint from the subject. Clinically significant abnormal findings from the physical or the neurological examinations will be reported as adverse events.

- e: Blood pressure and pulse.
- f: Weight and Height (without shoes) will be measured. Three measurements should be taken. Each measurement should be recorded as a separate entry on the Vital Sign eCRF.
- g: Unused study drug to be retrieved and study drug dispensed only for subject requiring dose increases at Unscheduled Visits.
- h: Clinical laboratory tests include hematology, blood chemistry including lipid panel, and urinalysis.
- i: Clinical laboratory test will be collected under fasting conditions.
- j: Performed if only an abnormality was noted at previous visit.

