## 8.2 SAFETY DATA HANDLING

### 8.2.1 Baseline safety

The baseline value for all safety endpoints will be the last non-missing measurement occurring prior to the first dose of the study medication.

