### 8.2.3 Handling of Replicate Data

A subject having an AE coded to the same preferred term more than once during the study will be counted only once in the incidence calculations for that AE. Similarly, if a subject has more than one AE in a single body system, the incidence will be counted only once for that body system. If a subject has the same AE more than once, the occurrence that is of greatest severity will be used in the calculation of the incidence of individual AE by severity. Similarly, the AE considered most closely related to study drug will be used in the calculation of incidence of individual AE by relationship.

For the laboratory, vital signs, ECG and other safety variables datasets, the measurement noted as the scheduled visit measurement will be used in the analysis. If more than one assessment is present at a scheduled visit, then the nearest assessment for evaluation

visit(day) will be used in the summaries of the actual values and changes from baseline. In the event of two assessments being equally close to the scheduled visit day, the last assessment will be used.

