If the window is not the baseline or the follow-up assessment, then the assessment closest to the scheduled assessment will be used in the summary tables. Note that if two assessments are equidistant from the scheduled assessment then the last assessment of the two (within the allowable window) will be used.

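### Neither SAP says how the triplicate height and weight readings become one value; applied literally, the selection rules use only the last entry

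*SAP*

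**What the plan says.** Protocol Table 4, note g (Core Study), says of weight and height: "Three measurements should be taken at each visit. Each measurement should be recorded as a separate entry on the Vital Sign eCRF". Table 5, note f (Extension A), repeats this: "Three measurements should be taken. Each measurement should be recorded as a separate entry on the Vital Sign eCRF". In the Core Study, weight is scheduled at every visit. Height is scheduled only at Visits 2 and 9 and at early discontinuation.

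Core SAP 8.2.3, on replicate data, covers laboratory, vital-sign, ECG and other safety datasets. It works in three steps:

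- First, "the measurement noted as the scheduled visit measurement will be used in the analysis".
- Next, "If more than one assessment is present at a scheduled visit, then the nearest assessment for evaluation" visit day is taken.
- Finally, "In the event of two assessments being equally close to the scheduled visit day, the last assessment will be used".

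The baseline rule in Core SAP 8.2.1 also yields one value: "The baseline value for all safety endpoints will be the last non-missing measurement occurring prior to the first dose of the study medication". Extension SAP 8.2.1 has the same rule, tied to the first Core Study dose. For visit windows, Extension SAP 8.2.2 says that "if two assessments are equidistant from the scheduled assessment then the last assessment of the two (within the allowable window) will be used", and Core SAP 8.2.2 agrees. In both SAPs the end-of-treatment value is the last one available.

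The growth paragraphs (section 5.6.6 of each SAP) ask for actual values, changes from baseline, percentiles and z-scores. They give no rule for combining readings. Section 9 of each SAP places the programming derivations in separate documents.

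**The concern.** Triplicate readings with separate entries are a deliberate choice, and its usual purpose is to reduce measurement error and expose mis-keyed values. The SAP rules were written to choose between visits or repeat assessments at different distances from a target day. Applied to three readings from one visit, they default to a single reading. The children and sites then carry the burden of triplicate measurement while the analysis gains nothing from it.

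Change in height and weight at Weeks 23 and 52 is part of secondary endpoint 4. For a child who completes the Core Study, the Week 23 height change would rest on two single entries, because no scheduled height in between could reveal an error. Weight also feeds the clinically notable vital-sign table (Table 1 in section 5.6.4 of each SAP), where the weight rows require a change of more than 7% and give no accompanying absolute value. At the minimum entry weight of 16 kg, 7% is 0.07 × 16 = 1.12 kg. One wrong entry could create or hide such a flag, and the SAPs do not say which of the three entries counts.

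**Working it through.** The plan states no figure on this point, so there is none to reproduce. The check has three parts.

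**1. Which reading the rules select.** The scheduled-visit step does not separate the three readings, because all belong to the same visit. The nearest-day step does not separate them either, because all have the same date. The tie-break then gives the last. The baseline, window and end-of-treatment rules also return one value. No step in either SAP forms a mean or median.

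**2. Readings used for the Week 23 change, per child (Table 4).**

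- Height: Visits 2 and 9, three readings each: 2 × 3 = 6.
- Weight: the last pre-dose visit (Visit 2) and Visit 9, three readings each: 2 × 3 = 6.
- TSH, fT3, fT4 and IGF-1: Visits 1 and 9, once each: 4 × 2 = 8.
- Height and weight: 12 readings, 4 used, 8 unused; 8/12 = 66.7%.
- Whole growth endpoint: 12 + 8 = 20 results, 12 used, 8 unused; 8/20 = 40%.

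**3. Precision.** Let Ve be the variance of one reading's measurement error, with errors independent, and Vc the true between-child variance of change.

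- Measurement-error variance of a change score: 2Ve with single readings, 2Ve/3 with means of three; ratio 3.
- Total variance of the change: Vc + 2Ve against Vc + 2Ve/3.
- With r = Ve/Vc, the SD ratio is √[(1 + 2r)/(1 + 2r/3)] and the equivalent loss of sample size is 1 − (1 + 2r/3)/(1 + 2r).

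The documents give neither Ve nor Vc, so r is assumed over a range:

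| r | SD ratio, single against mean of three | Equivalent sample-size loss |
|---|---|---|
| 0.01 | 1.007 | 1.3% |
| 0.05 | 1.032 | 6.1% |
| 0.1 | 1.061 | 11.1% |
| 0.5 | 1.225 | 33.3% |
| 1.0 | 1.342 | 44.4% |

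Worked for r = 0.1: (1 + 0.2)/(1 + 0.0667) = 1.125, whose square root is 1.061; the loss is 1 − 1.0667/1.2 = 11.1%. The loss approaches two thirds only as measurement error swamps true change. Errors shared by all three readings at a visit would reduce the gain from averaging.

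**The case against.** The strongest reply is that the SAPs are silent on triplicates and do not instruct anyone to drop readings. The tie-break is worded for two assessments compared by day, and three entries could be read as one assessment made up of three measurements. Reducing replicates to one value is also the kind of step that the programming specifications might define. This stands to the extent that a reader who infers an explicit instruction to keep only the last of three readings goes further than the text. It does not remove the point. If the tie-break does not reach triplicates, the SAPs have no rule for them. Section 8.2.3 states its own single-value rule and does not defer to the specifications, as the SAPs do for imputing missing dates. A specification that averaged would depart from that text.

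The second reply concerns size, and it largely stands. Growth is summarised descriptively, with no test or power attached. Assume a reading-error SD of 0.5 cm for height, which is not in the documents. The error SD of a change is then √2 × 0.5 = 0.71 cm with single readings and √(2/3) × 0.5 = 0.41 cm with means. Over 160 children, the error part of the standard error of the mean change is 0.71/√160 = 0.056 cm against 0.41/√160 = 0.032 cm. Over 36 children, the minimum for the younger partial-onset group, it is 0.12 against 0.07 cm. These figures scale in proportion to the assumed SD. They are small for a group mean; an individual child's flag is more exposed.

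Third, both SAPs allow outliers to be found by inspection and the data re-analysed without them. That helps, but it is optional and comes after the tables are made. It is also fair that a mean still carries one third of a mis-entry into the child's value.

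**Conclusion.** The point holds for height and weight. The protocol collects three readings per visit, neither SAP says how to combine them, and the rules as written lead to the last entry. That value is less precise and less resistant to error than the data already collected allow.

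Two stronger inferences are not supported. Two thirds of the growth endpoint's data are not lost: the share is two thirds of the height and weight readings but 40% of the endpoint's results, because thyroid tests and IGF-1 are not taken in triplicate. Nor is the variance of the growth change tripled: the factor of 3 is an upper figure for measurement-error variance alone and requires independent readings. The total loss is about 1% to 11% of equivalent sample size if error variance is 1% to 10% of true-change variance, which is an assumption.

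The analysis is descriptive, so no error rate or power is affected. The programming specifications were not available and may already contain a rule. This is a free improvement and no threat to the study's conclusions.

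**What to change.** Add one sentence to each SAP: the height or weight value at a visit, including baseline, is the mean of the readings available on that date, computed before any visit-selection rule is applied. The median is a reasonable alternative, since with three readings it resists a single mis-entry. Choose one and use it throughout. Add a data query for readings at the same visit that disagree by more than a limit fixed in advance. Use the resulting value for change from baseline, BMI, percentiles, z-scores and the 7% weight criterion. If the programming specifications already define such a rule, bring the SAP text into line with them.

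The cost is one sentence per SAP, one derivation step and the query check. No new data are needed, because all readings are already entered separately.

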### **Handling of prior/concomitant medication**

If the subject has taken the same concomitant medication (as coded to preferred WHO-drug term) more than once, the subject will be counted only once in the tabulation.

## **9 PROGRAMMING SPECIFICATIONS**

The rules for programming derivations and dataset specifications are provided in separate documents.

## **10 STATISTICAL SOFTWARE**

All statistical analyses will be performed using SAS v 9.3 or later.

## **11 MOCK TABLES, LISTINGS, AND GRAPHS**

The study TLG shells will be provided in a separate document, which will show the content and format of all tables, listings, and graphs in detail.

## 13 APPENDICES

### 13.1 Sponsor's Grading for Determining Markedly Abnormal Laboratory Results

The following table is of Sponsor's Grading for Laboratory Values from the version in the [protocol, Appendix 1](#).

#### Sponsor's Grading for Laboratory Values

	Grade 1	Grade 2	Grade 3	Grade 4
BLOOD/BONE MARROW				
Hemoglobin	<LLN – 10.0 g/dL <LLN – 100 g/L <LLN – 6.2 mmol/L	<10.0 – 8.0 g/dL <100 – 80 g/L <6.2 – 4.9 mmol/L	<8.0 g/dL <80 g/L <4.9 mmol/L; transfusion indicated	life-threatening consequences; urgent intervention indicated
Leukocytes (total WBC)	<LLN – $3.0 \times 10^9/L$ <LLN – 3000/mm 	<3.0 – $2.0 \times 10^9/L$ <3000 – 2000/mm 	<2.0 – $1.0 \times 10^9/L$ <2000 – 1000/mm 	< $1.0 \times 10^9/L$ <1000/mm 
Lymphocytes	<LLN – 800/mm  <LLN – $0.8 \times 10^9/L$	<800 – 500/mm  <0.8 – $0.5 \times 10^9/L$	<500 – 200/mm  <0.5 – $0.2 \times 10^9/L$	<200/mm  < $0.2 \times 10^9/L$
Neutrophils	<LLN – $1.5 \times 10^9/L$ <LLN – 1500/mm 	<1.5 – $1.0 \times 10^9/L$ <1500 – 1000/mm 	<1.0 – $0.5 \times 10^9/L$ <1000 – 500/mm 	< $0.5 \times 10^9/L$ <500/mm 
Platelets	<LLN – $75.0 \times 10^9/L$ <LLN – 75,000/mm 	<75.0 – $50.0 \times 10^9/L$ <75,000 – 50,000/mm 	<50.0 – $25.0 \times 10^9/L$ <50,000 – 25,000/mm 	< $25.0 \times 10^9/L$ <25,000/mm 
METABOLIC/LABORATORY				
Albumin, serum- low (hypoalbuminemia)	<LLN – 3 g/dL <LLN – 30 g/L	<3 – 2 g/dL <30 – 20 g/L	<2 g/dL <20 g/L	life-threatening consequences; urgent intervention indicated
Alkaline phosphatase	>ULN – 3.0×ULN	>3.0 – 5.0×ULN	>5.0 – 20.0×ULN	>20.0×ULN
ALT	>ULN – 3.0×ULN	>3.0 – 5.0×ULN	>5.0 – 20.0×ULN	>20.0×ULN
AST	>ULN – 3.0×ULN	>3.0 – 5.0×ULN	>5.0 – 20.0×ULN	>20.0×ULN
Bilirubin (hyperbilirubinemia)	>ULN – 1.5×ULN	>1.5 – 3.0×ULN	>3.0 – 10.0×ULN	>10.0×ULN
Calcium, serum-low (hypocalcemia)	<LLN – 8.0 mg/dL <LLN – 2.0 mmol/L	<8.0 – 7.0 mg/dL <2.0 – 1.75 mmol/L	<7.0 – 6.0 mg/dL <1.75 – 1.5 mmol/L	<6.0 mg/dL <1.5 mmol/L
Calcium, serum-high (hypercalcemia)	>ULN – 11.5 mg/dL >ULN – 2.9 mmol/L	>11.5 – 12.5 mg/dL >2.9 – 3.1 mmol/L	>12.5 – 13.5 mg/dL >3.1 – 3.4 mmol/L	>13.5 mg/dL >3.4 mmol/L
Cholesterol, serum-high (hypercholesterolemia)	>ULN – 300 mg/dL >ULN – 7.75 mmol/L	>300 – 400 mg/dL >7.75 – 10.34 mmol/L	>400 – 500 mg/dL >10.34 – 12.92 mmol/L	>500 mg/dL >12.92 mmol/L
Creatinine	>ULN – 1.5×ULN	>1.5 – 3.0×ULN	>3.0 – 6.0×ULN	>6.0×ULN
GGT (γ-glutamyl transpeptidase)	>ULN – 3.0×ULN	>3.0 – 5.0×ULN	>5.0 – 20.0×ULN	>20.0×ULN
Glucose, serum-high (hyperglycemia)	Fasting glucose value: >ULN – 160 mg/dL >ULN – 8.9 mmol/L	Fasting glucose value: >160 – 250 mg/dL >8.9 – 13.9 mmol/L	>250 – 500 mg/dL; >13.9 – 27.8 mmol/L; hospitalization indicated	>500 mg/dL; >27.8 mmol/L; life-threatening

### Sponsor's Grading for Laboratory Values

	Grade 1	Grade 2	Grade 3	Grade 4
				consequences
Glucose, serum-low (hypoglycemia)	<LLN – 55 mg/dL <LLN – 3.0 mmol/L	<55 – 40 mg/dL <3.0 – 2.2 mmol/L	<40 – 30 mg/dL <2.2 – 1.7 mmol/L	<30 mg/dL <1.7 mmol/L life-threatening consequences; seizures
Phosphate, serum-low (hypophosphatemia)	<LLN – 2.5 mg/dL <LLN – 0.8 mmol/L	<2.5 – 2.0 mg/dL <0.8 – 0.6 mmol/L	<2.0 – 1.0 mg/dL <0.6 – 0.3 mmol/L	<1.0 mg/dL <0.3 mmol/L life-threatening consequences
Potassium, serum-high (hyperkalemia)	>ULN – 5.5 mmol/L	>5.5 – 6.0 mmol/L	>6.0 – 7.0 mmol/L hospitalization indicated	>7.0 mmol/L life-threatening consequences
Potassium, serum-low (hypokalemia)	<LLN – 3.0 mmol/L	<LLN – 3.0 mmol/L; symptomatic; intervention indicated	<3.0 – 2.5 mmol/L hospitalization indicated	<2.5 mmol/L life-threatening consequences
Sodium, serum-high (hypernatremia)	>ULN – 150 mmol/L	>150 – 155 mmol/L	>155 – 160 mmol/L hospitalization indicated	>160 mmol/L life-threatening consequences
Sodium, serum-low (hyponatremia)	<LLN – 130 mmol/L	N/A	<130 – 120 mmol/L	<120 mmol/L life-threatening consequences
Triglyceride, serum-high (hypertriglyceridemia)	150 – 300 mg/dL 1.71 – 3.42 mmol/L	>300 – 500 mg/dL >3.42 – 5.7 mmol/L	>500 – 1000 mg/dL >5.7 – 11.4 mmol/L	>1000 mg/dL >11.4 mmol/L life-threatening consequences
Uric acid, serum-high (hyperuricemia)	>ULN – 10 mg/dL ≤0.59 mmol/L without physiologic consequences	N/A	>ULN – 10 mg/dL ≤0.59 mmol/L with physiologic consequences	>10 mg/dL >0.59 mmol/L life-threatening consequences

ALT = alanine aminotransferase (serum glutamic pyruvic transaminase), AST = aspartate aminotransferase (serum glutamic oxaloacetic transaminase), LLN = lower limit of normal, ULN = upper limit of normal, WBC = white blood cell.

Based on Common Terminology Criteria for Adverse events (CTCAE) Version 4.0. Published: May 28, 2009 (v4.03: June 14, 2010).

## 2 LIST OF ABBREVIATIONS AND DEFINITIONS OF TERMS

Abbreviation	Term
ABNAS	A-B neuropsychological assessment schedule
AE(s)	adverse event(s)
AED	antiepileptic drug
ALT	alanine aminotransferase
AST	aspartate aminotransferase
ATC	anatomical therapeutic class
BMI	body mass index
CBCL	Child Behavior Checklist
CGI	Clinical Global Impression
CGIC	Clinical Global Impression of Change
CGIS	Clinical Global Impression of Severity
CRF	case report form
C ss,av	average steady-state drug concentration
C-SSRS	Columbia-Suicide Severity Rating Scale
DMC	Data Monitoring Committee
ECG	Electrocardiogram
EEG	Electroencephalogram
EQ-5D-Y	EuroQol 5 Dimensions – Youth
FAS	Full Analysis Set
LOCF	last observation carried forward
MedDRA	Medical Dictionary for Regulatory Activities
GTC	Generalized Tonic-Clonic
HRQL	health-related quality of life
ICF	informed consent form
IP	Investigational products
LGPT	Lafayette Grooved Pegboard Test
LLN	lower limit of normal
LNH	low/normal/high
MedDRA	Medical Dictionary for Regulatory Activities
PD	Pharmacodynamics

Abbreviation	Term
PGTC	primary generalized tonic-clonic
PK	Pharmacokinetics
POS	partial-onset seizures
PT	preferred term
QTc	corrected QT interval (time from the beginning of the QRS complex to the end of the T wave, corrected for heart rate)
SAE	serious adverse event
SAP	statistical analysis plan
SI	Système International
SMQ	standardized MedDRA queries
SOC	system organ class
TEAE	treatment-emergent adverse event
TEMAV	treatment-emergent markedly abnormal laboratory values
TLG	tables, listings, and graphs
ULN	upper limit of normal
WHO	World Health Organization

### 3 INTRODUCTION

The purpose of this statistical analysis plan (SAP) is to describe the procedures and the statistical methods that will be used to analyze and report results for the Extension Phase of Eisai Protocol E2007-G000-311. The SAP for the Core Study of Eisai Protocol E2007-G000-311 is a separate document.

#### 3.1 Study Objectives

##### 3.1.1 Primary Objective(s)

To evaluate the safety and tolerability of E2007/perampanel oral suspension when administered as an adjunctive therapy in children (ages 4 to <12 years) with inadequately controlled partial-onset seizures (POS) or primary generalized tonic-clonic seizures (PGTC)

##### 3.1.2 Secondary Objectives

1. To characterize the PK of perampanel and the relationship between perampanel plasma concentrations, efficacy, and safety using population PK/PD modeling
2. To evaluate the effects of perampanel on cognition, behavior, visuomotor skills, and growth and development in children during short-term (23 weeks) and long-term (up to 52 weeks) treatment
3. To evaluate the frequency of EEG abnormalities during awake and sleep state during 52 weeks of treatment
4. To evaluate suicidal ideation and suicidal behavior in children 6 years to less than 12 years as measured by the Columbia-Suicide Severity Rating Scale (C-SSRS) during 52 weeks of treatment
5. To evaluate the efficacy of perampanel as measured by the median percent change per 28 days in seizure frequency, by the proportion of responders ( $\geq 25\%$ ,  $\geq 50\%$ , and  $\geq 75\%$ ), and by the proportion of subjects who are seizure-free for POS, PGTC, and Generalized Tonic-Clonic (GTC) seizures
6. To evaluate, in Japanese subjects, the efficacy of perampanel on partial onset seizures(POS) in the present study as compared with placebo in Study E2007-J000-335
7. To assess the effects of perampanel on the Clinical Global Impression (CGI), CGI of Severity (CGIS) and CGI of Change (CGIC)

### 3.1.3 Exploratory Objective

To assess the impact of perampanel on the health utility of children using the Euroqol 5 Dimensions-Youth (EQ-5D-Y) scale.

